with etelcalcetide improves bone hardness and mineralization using Ramen/nanoindentation and remodeling by histomorphometry using the quadruple label transiliac crest bone biopsy method in 20 ESKD patients with severe HPT.

Figure 2. Study timeline.

[figure not shown]

Table 1: Data Collection at each Study Visit

	Baseline	3 Months	9 Months
Informed consent	x		
Medical History	x		x
Physical Exam	x		x
Kt/V	x	x	x
Biomarkers of bone formation and resorption (BSAP, P1NP, CTX)	x	x	x

Procedures. This is a single-arm prospective cohort study to test the effects of 6-months of treatment with etelcalcetide on bone-tissue properties. We will obtain a single quadruple label bone biopsy to assess longitudinally the effects of 6-months of treatment with etelcalcetide on bone properties at the tissue level.

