We will enroll 20 adult patients with ESKD on hemodialysis who are scheduled to receive etelcalcetide for the treatment of HPT per standard of care. These 20 patients with ESKD will be treated with etelcalcetide to maintain levels of PTH between 300 and 400 pg/mL, which is at the mid-range of the KDIGO recommended range (2-9 times the ULN for the PTH assay¹) for 6 months. Patients will be identified for inclusion based on clinical need for the treatment of severe HPT and high turnover bone disease and only patients whose treating physician plans to initiate etelcalcetide will be included. HPT will be defined by the KDIGO guidelines (PTH >9-times the ULN for the PTH assay¹) and high turnover bone disease will be defined by a total alkaline phosphatase level \geq upper tertile of the reference range for the assay. At study start, patients will undergo the initial double labeling procedure with tetracycline (TCN; 3-days of TCN followed by 12-days off TCN followed by 3-days of TCN); during the labeling period etelcalcetide will not be administered (**Figure 2**). Patients will then undergo a 3-month etelcalcetide dose-titration phase to ensure that PTH levels are consistently maintained within target range (300-400 pg/mL), followed by a 6-month treatment (maintenance) phase. At the study endpoint (6-months of treatment), the final set of labels for transiliac crest bone biopsy will be given (3-days of demeclocycline followed by 12-days off demeclocycline followed by 3-days of demeclocycline) and bone biopsy will occur 5-days after the last dose of demeclocycline. During the final labeling period, the dose of etelcalcetide will continue to target the goal PTH level and the patient will continue to be managed as clinically indicated. The quadruple label approach permits longitudinal assessment of both dynamic indices of histomorphometry and bone-tissue level properties pre- and post-intervention, with the use of a single biopsy. The first label (TCN) is given prior to the initiation of etelcalcetide and the second label (demeclocycline) is given after 6-months of treatment (maintenance) with etelcalcetide. The fluorescence of tetracycline and demeclocycline differs, permitting differentiation of the labels under fluorescence microscopy and determination of dynamic indices of histomorphometry pre- and post-intervention. To assess bone tissue level effects of treatment, we will use a Raman/Nanoindentation system. This system allows the differentiation of tetracycline (pre-treatment) and demeclocycline (post-treatment) labels and permits precise measurement of localized bone tissue properties (e.g., mineral/matrix, collagen) and indentation properties (e.g., hardness) within these regions. Additionally, we will use 3-dimensional micro-CT (μ CT) imaging (resolution 3 μm^3) to obtain more complete structural indices from the bone biopsy specimens at the 6-month time point. Patients will have blood collected and stored at -80°C, at baseline (pre-treatment) and after 3- and 6-months of treatment (i.e., maintenance phase) (**Table 1**). Blood will be assayed for calcium, phosphorus, PTH, vitamin D metabolites, bone formation (bone specific alkaline phosphatase [BSAP], procollagen type-1 N-terminal propeptide [P1NP]) and resorption (C-Telopeptide [CTX]) markers, FGF-23 and sclerostin.

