
Bone biopsy with quantitative histomorphometry and nanoindentation/Raman spectroscopy. After bone biopsy, the specimens will be transferred to [name] laboratory for tissue analysis (described below).

μ CT. 3D trabecular and cortical structure will be assessed on biopsies before embedding using a Skyscan 1172 system (scanning resolution of 6 μm^3). Outcome measurements will include both cortical parameters (porosity [%], mineralization [average value and variation] and thickness) and trabecular parameters (BV/TV, trabecular number, separation, thickness, and connectivity density) using manufacturer software and standard analytical protocols. At study initiation, we will perform short-term precision measurements on selected structural and mechanical properties. QC procedures are enforced by the in-house software system, and include weekly scanning of a QA/ μ CT phantom. The software system's QA analysis monitors scanner performance and normalizes results for any fluctuations. QA data and specimen results can be exported to SAS or Excel.

Quantitative histomorphometry. Following CT scans, specimens will be embedded in methyl methacrylate using standard protocols. Sections will be cut with a rotary microtome and either left unstained or stained with McNeal tetracrome or tartrate resistant acid phosphatase for analysis. Histomorphometric indices will be defined in accordance with the American Society for Bone and Mineral Research⁵. The following histomorphometric indices will be measured or calculated: osteoid surface, area, and width; osteoclast surface, eroded surface, resorption depth, resorption period; cancellous wall width, mineral apposition rate, bone formation rate, adjusted

PTH, Vitamin D metabolites, Serum calcium and phosphorus, FGF-23, Sclerostin, T50	x	x	x
Bone biopsy Labeling (for participants enrolled in Aim 1)	x		x
Bone biopsy (for participants enrolled in Aim 1)			x
Imaging: DXA and HR-pQCT	x		x
AGE Reader	x		x

apposition rate, mineralization lag time, activation frequency. Note: architectural properties (BV/TV, porosity, etc) will not be collected, as these will be obtained from CT as above.

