HR-pQCT Finite Element Analysis (FEA). [name] will estimate mechanical competence (strength) from HR-pQCT images. Each image is converted to a μ FE model by directly converting bone voxels to 8-node elastic brick elements. A uniaxial displacement equaling 1% of the bone segment height is applied perpendicularly to the distal surface of the radius or tibia while the proximal surface is imposed with zero displacement along the same direction. The total reaction force is calculated from the linear μ FE analysis, and the axial stiffness is calculated as the reaction force divided by the imposed displacement.

HR-pQCT Cortical Porosity. [name] will conduct analyses of cortical porosity using methods that have been described and validated in recent publications⁸.

Hypothesis 3. Etelcalcetide decreases serum calcification propensity in patients with ESKD.

Aim 3. To test if 6-months of treatment with etelcalcetide decreases serum propensity to calcify soft tissues. In a single-arm study of 35 patients with ESKD treated with 6-months of etelcalcetide, we will measure T50, calcitropic hormones, serum calcium and phosphorus, bone turnover markers, FGF-23 and Sclerostin pre-treatment and 3- and 6-months after treatment.

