Procedures. We will enroll 35 patients (20 from Aim 1 and 15 *de novo*) into this prospective single-arm cohort study to test the hypothesis that 6 months of treatment (maintenance) with etelcalcetide will decrease the propensity to calcify soft tissues as measured by T50. Similar to **Aim 1**, eligibility for enrollment into **Aim 3** will be based on a PTH level >9-times the ULN for the PTH assay (**Figure 1**), as well as their treating physician's plan to initiate etelcalcetide per standard of care. However, the presence of high turnover bone disease based on total alkaline phosphatase will not be a criterion for enrollment into **Aim 3**. Furthermore, all patients enrolled in **Aim 1** will be automatically enrolled into **Aim 3** unless they choose to opt-out of **Aim 3**. Thus, we will use the biochemical data from the 20 enrollees participating in **Aim 1** and enroll an additional 15 patients to be treated with etelcalcetide. As per **Aim 1** (**Figure 2**), after enrollment, patients will undergo a 3-month dose titration phase to ensure that PTH levels are stability maintained within the target range (300-400 pg/mL), followed by a 6-month treatment (maintenance) phase. Patients will have blood collected and stored at -80°C, at baseline (pre-treatment) and after 3- and 6-months of treatment (i.e., maintenance phase). Blood will be assayed for T50, calcium, phosphorus, PTH, vitamin D metabolites, bone formation (BSAP, P1NP) and resorption (CTX) markers, FGF-23 and sclerostin. We will assess the effect of treatment on changes in levels of T50, a clinically relevant biomarker of calcification propensity^{9, 10}. We will also determine relationships between changes in T50 and changes in phosphorus, calcium, bone turnover markers and calcitropic hormones.

Exploratory. None

Primary and Secondary Endpoints for Each Aim

Aim 1

1. Primary Endpoints: Hardness
2. Secondary Endpoints: Bone formation rate, mineralization density

Aim 2

1. Primary Endpoints: Changes in: (a) femoral neck areal BMD by DXA and (b) radius failure load by HR-pQCT
2. Secondary Endpoints: Changes in: (a) spine, total hip, and one-third and ultradistal radius BMD by DXA and (b) radius and tibia cortical density, thickness, porosity and tissue mineral density, and trabecular density, thickness, number and spacing

Aim 3

1. Primary Endpoint: Change in T50 (percent and absolute)
2. Secondary Endpoints: Changes in PTH, calcitropic hormones, FGF-23, Sclerostin, calcium and phosphorus

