For Aim 3. A two-tailed dependent T-test of the change in primary calcification propensity (T50) and secondary biochemical indices (calcitropic hormones, FGF-23, sclerostin, calcium and phosphorus) from pre-treatment baseline to the 6-month endpoint will be reported with an alpha-level of 5% as the criterion for statistical significance. Secondary exploratory analyses will assess the within-subject temporal course of change in the biochemical outcome with linear mixed models for repeated measures with time as a fixed effect (0, 3 and 6 months); the baseline value of the dependent variable entered as a continuous covariate; and a covariance structure determined by empirical testing performed prior to inferential testing. We will also assess whether the **Aim 1** participants differ from the patients recruited *de novo* for **Aim 3** with an independent T-test both of the two groups' baseline values and of the two groups' change in values from baseline to the 6-month endpoint. We will explore the covariances between changes in T50 and other biochemical markers of bone turnover and calcitropic hormones with simple and multiple regression with synchronized and lagged observations in time to determine whether leading, cotemporaneous or following patterns exist among these measures.

Subject Recruitment and Selection

Study site and number of patients eligible for enrollment. ESKD patients receiving hemodialysis at the Rogosin Institute, meeting enrollment criteria, and whose treating physicians intend to initiate treatment with etelcalcetide will be asked to participate in this study. Rogosin is the largest provider of hemodialysis in New York City and provides hemodialysis services to over 1300 patients. Approximately 25% of patients at Rogosin have PTH levels > 9-times the ULN for the PTH assay. Therefore, there are adequate numbers of patients at Rogosin who may be able and willing to participate in this prospective cohort study.

Enrollment Criteria

Inclusion criteria

For All Aims:

1. Patient has provided informed consent.
2. Patient is 18 years of age or older.
3. Patient must be receiving maintenance hemodialysis for at least 3 months, with adequate hemodialysis with a delivered Kt/V 1.2 or urea reduction ratio (URR) 65% within 4 weeks prior to screening laboratory assessments.
4. Dialysate calcium concentration must be stable for at least 4 weeks prior to screening laboratory assessments.

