*** Administration and Dosing of Etelcalcetide and Management of Hypocalcemia and Over-suppression of PTH**

The protocol will allow for changes in the dose of etelcalcetide, vitamin D sterols, calcium supplements and phosphate binders based on the levels of serum PTH, calcium and phosphorus that are obtained on a monthly basis as part of the standard of care monthly lab set for patients on hemodialysis.

- 1) Administration: by intravenous bolus injection into the venous line of the dialysis circuit at the end of hemodialysis treatment during rinse back or intravenously after rinse back.
- 2) Initiation and dose adjustment of etelcalcetide
 - a) Starting dose of etelcalcetide: 5.0 mg
 - b) Maximum dose of etelcalcetide: 15.0 mg
 - c) Dose adjustments: increase in 2.5-5.0 mg increments at weeks 4, 8, 12 during the titration phase and at the time of the monthly lab sets during the treatment phase based on PTH and calcium.
- 3) Missed doses
 - a) If a regularly scheduled hemodialysis treatment is missed, do not administer any missed doses.
 - i) Resume etelcalcetide at the end of the next hemodialysis treatment at the prescribed dose.
 - ii) If doses of etelcalcetide are missed for more than 2 weeks, re-initiate etelcalcetide at the recommended starting dose of 5 mg (or 2.5 mg if that was the patient's last dose).
- 4) Management of hypocalcemia
 - a) Monitor corrected serum calcium one-week after starting or changing a dose of etelcalcetide
 - b) Drop in corrected serum calcium WNL of the reference range
 - i) no dose change
 - c) Drop in serum calcium < LLN of the reference range but ≥ 7.5 mg/dL without symptoms of hypocalcemia
 - i) increase calcium in dialysate to the next highest level and/or start calcium oral supplement and monitor as per HD unit safety protocol
 - (1) If calcium has normalized and PTH remains within the target range: no dose change
 - (2) If calcium has normalized but PTH has risen above the target range: increase dose by 2.5 mg and monitor PTH and calcium per HD unit safety policy
 - (a) If calcium and PTH are at goal: no dose change
 - (b) If calcium < LLN but ≥ 7.5 mg/d without symptoms: increase calcium in dialysate and/or start calcium oral supplement and monitor as per HD unit safety protocol
 - (i) If calcium remains < LLN but ≥ 7.5 mg/d, changes in levels of active vitamin D sterols can be implemented

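### Table 1 puts the only intermediate T50 draw at month 3 and the text puts it at month 6; the exploratory model using it enters baseline as both outcome and covariate

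*Combined protocol and SAP*

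**What the plan says.** All references are to the combined protocol and SAP.

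- **Table 1**, titled "Table 1: Data Collection at each Study Visit", has three columns: Baseline, 3 Months and 9 Months. The row "PTH, Vitamin D metabolites, Serum calcium and phosphorus, FGF-23, Sclerostin, T50" is marked in all three, as is the row of bone turnover markers.
- **Aim 1, Procedures** describes a 3-month titration phase and then a 6-month maintenance phase. Blood is drawn before treatment and "after 3- and 6-months of treatment (i.e., maintenance phase) (Table 1"; the sentence cites the table as its source.
- **Aim 3, Procedures** repeats the schedule: "at baseline (pre-treatment) and after 3- and 6-months of treatment (i.e., maintenance phase".
- **Aim 3, statement of the aim** gives "FGF-23 and Sclerostin pre-treatment and 3- and 6-months after treatment", with no time origin.
- **Statistical methods, For Aim 3** tests T50 with a paired t-test from baseline to the end. It then adds an exploratory mixed model "with time as a fixed effect (0, 3 and 6 months); the baseline value of the dependent variable entered as a continuous covariate", with the covariance structure picked from the data, and regressions on same-time and lagged values.
- **Administration and Dosing of Etelcalcetide** sets dose steps as "increase in 2.5-5.0 mg increments at weeks 4, 8, 12 during the titration phase" and relies on "serum PTH, calcium and phosphorus that are obtained on a monthly basis as part of the standard of care monthly lab set".
- **Early Study Cessation Clause** sends a patient who is transplanted after at least 3 months on drug to end-of-study procedures, including labs, within 4 weeks of transplant.

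**The concern.** Table 1 and the procedures name different months for the only intermediate research sample, and one of them cites the other as its source. The two months fall in different treatment phases. Month 3 is the end of titration, at about the week-12 dose step; month 6 is the middle of maintenance. PTH, calcium and phosphorus are measured monthly in routine care, so clinical values exist for either month. The plan gives no such routine source for T50, FGF-23, sclerostin and the turnover markers, so a sample drawn at the wrong month is lost. The lagged regressions look for leading and following patterns, and their lag from the middle to the last visit would be 6 or 3 months depending on which page staff follow.

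The second, smaller issue is the mixed model. Time 0 is a level of the outcome, and the same value is also a predictor. That makes the planned data-driven choice of covariance structure unworkable for some candidates and misleading for others.

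**Working it through.** **1. Schedule.** Inputs: titration 3 months, maintenance 6 months (Aim 1 and Aim 3 Procedures); Table 1 columns 0, 3 and 9.

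| Time origin for the text's 3 and 6 months | Middle draw | Last draw | Agrees with Table 1 (3, 9)? |
|---|---|---|---|
| Start of maintenance | 3 + 3 = 6 | 3 + 6 = 9 | last only |
| First dose | 3 | 6 | middle only |

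Table 1's last visit is reproduced by 3 + 6 = 9. Its middle visit is not, and no single origin gives both 3 and 9.

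The real intervals are 3 then 6 months (Table 1) or 6 then 3 months (text). The model's 0/3/6 labels suggest two equal intervals, which neither schedule has. With visit categorical, the labels change no estimate. If time were fitted as numeric, a steady change of 1 unit per month would give a slope of 1.5 under either schedule: regressing (0, 3, 9) or (0, 6, 9) on (0, 3, 6) gives 27/18 = 1.5.

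As an illustration, suppose T50 moved linearly to month 9 (an assumption) and changed by the 0.7 SD of the Aim 3 sample-size section. The middle draw would show 0.7 × 3/9 = 0.23 SD or 0.7 × 6/9 = 0.47 SD.

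Two related points:
- Table 1 does not say whether months run from baseline or from first dose. In Aim 1, labeling without drug takes 3 + 12 + 3 = 18 days, which patients recruited only for Aims 2 and 3 do not have.
- If a transplant falls between about months 3 and 5, the end-of-study labs come before a month-6 draw is due and the middle value is lost. Under Table 1 it has already been taken.

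**2. Unbounded likelihood.** For a fixed baseline slope b, the residuals are a linear map of the data: (y0, y1, y2) → ((1−b)y0, y1−b·y0, y2−b·y0). Its determinant is 1−b. With an unstructured covariance the maximised ML log-likelihood therefore changes by −n ln(1−b). At n = 35 that is 35 × ln 10 = 80.6 for each tenfold step of b toward 1 (REML: 33 × ln 10 = 76.0). In one simulated data set it went from −33 (b = 0) to 48 (0.9), 209 (0.999) and 370 (0.99999). The time contrasts and their SEs are the same at every b. The same divergence occurs for any structure with a free month-0 variance, such as heterogeneous CS or heterogeneous AR(1).

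**3. Choice between structures with finite fits.** Homogeneous compound symmetry (CS) and AR(1) can both be fitted. Under CS with complete data, the covariate leaves contrasts and SEs unchanged but absorbs the correlation: at a true correlation of 0.5, the fitted residual correlation is 0.49 without it and 0.09 with it. Selection between CS and AR(1) was simulated with n = 35, three categorical visits, no true change, complete data, REML and 20,000 trials per scenario (Monte Carlo SE about 0.2 points). The two structures have equal parameter counts, so AIC, BIC and likelihood agree. Assumed here, because the plan gives none of them: the correlations, the candidate pair and equally spaced AR(1).

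| Assumed correlation | 0.3 | 0.6 | 0.8 |
|---|---|---|---|
| CS true: CS chosen, no covariate | 74% | 87% | 91% |
| CS true: CS chosen, with covariate | 26% | 4% | 2% |
| CS true: type I error, with covariate | 4.9% | 4.2% | 3.4% |
| AR(1) true: true SE of last minus baseline | 0.228 | 0.191 | 0.143 |
| AR(1) true: mean SE, no covariate | 0.220 | 0.185 | 0.140 |
| AR(1) true: mean SE, with covariate | 0.210 | 0.170 | 0.126 |
| AR(1) true: type I error, no covariate (68 df) | 5.9% | 5.8% | 5.7% |
| AR(1) true: type I error, with covariate (68 df) | 7.1% | 7.9% | 8.4% |

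The true SE under AR(1) is √(2(1−ρ²)/35). With the covariate the SE is 8, 11 and 12% too small. The excess type I error due to the covariate is 1.2, 2.1 and 2.7 points. Imposing CS when AR(1) is true gives 7.3, 8.9 and 9.9% with or without the covariate, so the covariate does no more harm than that. The paired t-test stays at 4.8 to 5.3% in all six scenarios.

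**The case against.** The strongest objection is reach. The primary T50 test and the secondary biochemical tests compare baseline with the last draw, which is month 9 under both schedules. Only an exploratory mixed model and exploratory regressions use the middle draw. This stands, and it limits the weight of the point.

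Figure 2, the study timeline, could not be read here and may tell staff which month is meant. That would lower the practical risk. It would not make Table 1 agree with the text that cites it.

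On the model, the list of 0, 3 and 6 months could be read as naming visits, with month 0 entering only as the covariate. The literal wording puts 0 among the levels of time, so the ambiguity itself needs removing. A likelihood without a maximum would probably show up as a fitting failure before any inference, and with an unstructured covariance the contrasts and SEs are unharmed. The type I figures rest on structures and correlations the plan does not name, and equal spacing matches neither schedule. Rerunning with exponential decay at 0/3/9 and 0/6/9 still gives an excess of about 1 to 3 points.

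Two details should not be pressed. Eighteen days is the length of labeling, not a proven maximum gap between baseline and first dose. The transplant case is narrow, since scheduled transplants are excluded.

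**Conclusion.** The concern holds. The schedule conflict follows from the plan's own phase lengths and needs no assumption: the middle draw is at month 3 or month 6, and the gap to the last draw is 6 or 3 months. As written, Table 1 and the procedures cannot both be followed, and the research-only samples depend on which one staff use.

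The model defect also holds on the literal wording but is minor. The unbounded likelihood is exact algebra. The distorted selection and the excess of about 1 to 3 points of type I error depend on the assumed correlations, on CS and AR(1) as the candidates, and on AR(1) being true. The primary paired t-test and the complete-data point estimates are unaffected. This should be corrected, but it does not threaten the main conclusion of Aim 3.

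**What to change.** - **Schedule.** Make Table 1, the Aim 1 and Aim 3 procedures, the Aim 3 statement and the model's time labels name one month for the middle draw, counted from first dose. The investigators must decide which month is intended; the documents do not settle it.
- **Elapsed time.** Record actual months since first dose for every draw, including for patients who leave under the Early Study Cessation Clause. Use them wherever time is numeric or a lag is a duration.
- **Model.** Keep all three visits as outcomes, treat visit as categorical and drop the baseline covariate. Name an unstructured covariance in advance; with three visits it has 6 parameters. With complete data and 35 − 1 = 34 denominator df, it reproduces the paired t-test for last minus baseline.
- **Alternative to limit.** A model of post-baseline values only, with baseline as covariate, should be used only to compare the middle and last visits. In a single arm it treats the sample baseline mean as fixed, so its SE for mean change from baseline is too small by the factor √((1+r)/2). That is 0.81, 0.89 and 0.95 at assumed baseline-to-last correlations of 0.3, 0.6 and 0.8, with simulated type I error of 11.1, 8.0 and 5.9% (33 df).

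The cost is one correction to the table or the text before middle draws are scheduled, and one sentence in the statistical section. No visits or samples are added.
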